## 8.3. Variables

All data will be extracted from the Medicare Database (Section 8.4). Baseline variables will be measured for the prior 12 months through the index date (exclusive of the index date). All relevant ICD-9-CM, ICD-10-CM, and CPT codes are available in the Appendix.

Variable a	Role	Operational definition
Age	Baseline characteristic and potential predictor	Age will be defined as of the index date, retained in the dataset as continuous, and divided by the following age groups: 65-74, 75-84, and $\geq$ 85 years.
Sex	Baseline characteristic and potential predictor	A flag will be created for female beneficiaries on the index date and reported as a percentage.
Race/ethnicity	Baseline characteristic and potential predictor	A flag will be created for White, Black, Hispanic, and other races/ethnicities on the index date.
US geographic region	Baseline characteristic and potential predictor	The US will be divided into 5 regions: Northeast, South, North Central, West, and Other. Geographic region will be captured from enrollment data.

Table 1	. Baseline	Variables
---------	------------	-----------

Do not distribute for purposes outside of specific activities related to development of FDAMAs114 compliant pieces. Content within this protocol is subject to change based on communication planning and input by external review committees.

#### Apixaban

NON-INTERVENTIONAL	STUDY DDOTOCOL
NON-INTERVENTIONAL	STUDIIKUIUCUL

Variable a	Role	Operational definition	
Index year	Baseline characteristic and potential predictor	A flag will be created for patients with index date in the year of 2013-2016.	
Medicaid dual eligibility	Baseline characteristic and potential predictor	A flag will be created for patients with Medicaid dual eligibility.	
Part-D low income subsidy	Baseline characteristic and potential predictor	A flag will be created for patients with a Part-D low income subsidy.	
Baseline Deyo-Charlson comorbidity index score	Baseline characteristic and potential predictor	The Deyo-Charlson comorbidity index score will be created during the baseline.	
Baseline CHADS2 score	Baseline characteristic and potential predictor	The CHADS 2 score will be used to analyze the effect of stroke risk stratification on OAC use. The maximum score is 6. CHADS 2 scores: 2-3, 4-5, and $\geq 6$ .	
Baseline CHA2DS2-VASc score	Baseline characteristic and potential predictor	The CHADS 2 VASc score will also be used as indicated above. The maximum score is 9. CHADS 2 -VASc scores: 2-3, 4-5, and $\geq 6$ .	
HAS-BLED score	Baseline characteristic and potential predictor	The HAS-BLED score will be used to estimate the risk of major bleeding. As the INR value is not available in the databases, a modified HAS-BLED score was calculated with a range of 0 to 8.	
Baseline prior bleed	Baseline characteristic and potential predictor	A flag will be created for patients with a bleeding- related claim during the baseline period.	
Baseline prior stroke/SE	Baseline characteristic and potential predictor	A flag will be created for patients with a stroke/SE claim during the baseline period.	
Obesity	Baseline characteristic and potential predictor	A flag will be created for patients with obesity claims during the baseline.	

Do not distribute for purposes outside of specific activities related to development of FDAMAs114 compliant pieces. Content within this protocol is subject to change based on communication planning and input by external review committees.

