# 1. LIST OF ABBREVIATIONS

Abbreviation	Definition
AE	Adverse Event
AF	Atrial Fibrillation
CAD	Coronary Artery Disease
CCI	Charlson Comorbidity Index
CHADS 2	Congestive heart failure, Hypertension, Age ≥75 years, Diabetes mellitus, Stroke
CHA 2 DS 2 - VASc	Congestive heart failure, Hypertension, Age ≥75 years, Diabetes mellitus, Stroke, Vascular disease, Age 65-74 years, Sex category
CHF	Congestive Heart Failure
CI	Confidence Interval
CMS	Centers for Medicare & Medicaid Service
СРІ	Consumer Price Index
DME	Durable Medical Equipment
DOACs	Direct Oral Anticoagulants
ER	Emergency Room
FFS	Fee-For-Service
HAS-BLED	Hypertension, Abnormal renal/liver function, Stroke, Bleeding history or predisposition, Labile international normalized ratios, Elderly, Drugs/alcohol

Do not distribute for purposes outside of specific activities related to development of FDAMAs114 compliant pieces. Content within this protocol is subject to change based on communication planning and input by external review committees.

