#### Apixaban

NON-INTERVENTIONAL STUDY PROTOCOL

plan enrollment with medical and pharmacy benefits (Medicare parts A, B, and D) after the index date;

Note: Revised from no requirement for continuous health plan enrollment post-index date to generate comparable cohorts.

- 3) Patients had CHA2DS2-VASc score  $\geq$ 2 during 12 months on or before the index date;
- 4) Aged  $\geq 65$  years on the index date.

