# Logistic Regression: Predictors for OAC Treatment/non-treatment (Primary Objectives)

A logistic regression will be used to examine risk factors associated with OAC treatment (OAC, DOAC, or warfarin)/non-treatment with OACs and DOAC treatment/warfarin treatment. Predictor data will be examined during the 12 months baseline period before the index date.

Stepwise model selection will be used to identify risk factors. The final covariate lists will be finalized based on clinical rationale and model fitting.

Odds ratios, p-values, and 95% confidence intervals (CIs) for all model covariates will be provided. Diagnostic tests will be performed for the multivariate models. Hosmer-Lemeshow tests will be performed and the area under the Receiver Operating Characteristic curve will be checked.

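### Table 1 bands CHADS2 as 2-3, 4-5 and ≥6, so eligible patients who score 0 or 1 fall in no category

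*Protocol*

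**What the plan says.** Protocol section 8.3, Table 1, lists the baseline CHADS2 score as a baseline characteristic and a possible predictor. It states that the "score will be used to analyze the effect of stroke risk stratification on OAC use. The maximum score is 6", and then sets the groups: "scores: 2-3, 4-5, and" ≥6. The next row gives CHA2DS2-VASc a maximum of 9 and the same three groups.

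Section 1 defines the two scores. CHADS2 is built from "Congestive heart failure, Hypertension, Age ≥75 years, Diabetes mellitus, Stroke". CHA2DS2-VASc is built from "Congestive heart failure, Hypertension, Age ≥75 years, Diabetes mellitus, Stroke, Vascular disease, Age 65-74 years, Sex category".

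Section 8.2.1.1 puts the entry threshold on CHA2DS2-VASc alone: criterion 3 requires a score of at least 2 "during 12 months on or before the index date", and criterion 4 requires age 65 or over. The abstract repeats the CHA2DS2-VASc threshold. Neither place sets a minimum for CHADS2.

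For the primary objective, section 8.7 plans logistic regression: "Stepwise model selection will be used to identify risk factors". The final covariate list is left to clinical rationale and model fit.

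**The concern.** The CHADS2 bands start at 2, but nothing in the protocol keeps patients with 0 or 1 out of the cohort. The bands appear to have been carried over from CHA2DS2-VASc, where a lower limit of 2 matches the entry criterion and the range up to 9 gives the top band real width. On a score with a maximum of 6, the ≥6 band can hold only the value 6.

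This is more than untidy labelling because CHADS2 is in the table to relate stroke risk to OAC use, which is the subject of the primary objective. Two things follow if the bands are coded as written:

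- The baseline table has CHADS2 categories that do not sum to the cohort.
- In a model with banded CHADS2 among its candidates, patients without a band carry a missing value. Complete-case fitting drops them, even if stepwise selection does not keep CHADS2. If they are placed in an existing band instead, the odds ratios no longer describe the categories that Table 1 names.

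**Working it through.** **Inputs.** The components come from section 1, the maxima (6 and 9) and bands from Table 1, and the entry criteria from section 8.2.1.1. The protocol does not print point weights. I infer them from the score names and maxima, and take the sex point to be for women. If it went to men, the profile counts would be the same and only the examples would swap sex.

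**Reproducing the stated maxima.**
- CHADS2: heart failure 1 + hypertension 1 + age ≥75 1 + diabetes 1 + stroke 2 = 6, as stated.
- CHA2DS2-VASc: 1 + 1 + 2 (age ≥75) + 1 + 2 (stroke) + 1 (vascular) + 1 (sex) = 9, as stated.

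**Counting profiles.** There are seven yes/no components (heart failure, hypertension, diabetes, stroke, vascular disease, female sex, and age ≥75 versus 65-74), so 2^7 = 128 profiles. Only one fails CHA2DS2-VASc ≥2: a man aged 65-74 with nothing else, who scores 1. That leaves 127.

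CHADS2 ignores sex and vascular disease, so each CHADS2 pattern occurs in 2 × 2 = 4 profiles. By the number of the four one-point items present (heart failure, hypertension, age ≥75, diabetes), there are 1, 4, 6, 4 and 1 patterns with 0, 1, 2, 3 and 4 items.

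| CHADS2 | Patterns | Eligible profiles | Band in Table 1 |
|---|---|---|---|
| 0 | no stroke, 0 items | 1 × 4 − 1 ineligible = 3 | none |
| 1 | no stroke, 1 item | 4 × 4 = 16 | none |
| 2-3 | no stroke, 2-3 items (10); stroke, 0-1 items (5) | 15 × 4 = 60 | 2-3 |
| 4-5 | no stroke, 4 items (1); stroke, 2-3 items (10) | 11 × 4 = 44 | 4-5 |
| 6 | stroke, 4 items (1) | 1 × 4 = 4 | ≥6 |

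The total is 3 + 16 + 60 + 44 + 4 = 127, and 3 + 16 = 19 profiles have no band. The same bands applied to CHA2DS2-VASc cover all 127 (22 + 56 + 49).

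**Examples of eligible patients without a band** (CHA2DS2-VASc, CHADS2):
- woman 65-74, no comorbidity: 2, 0
- man 65-74, hypertension only: 2, 1
- man ≥75, no comorbidity: 2, 1
- woman ≥75, vascular disease only: 4, 1

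**Share of patients.** The protocol gives no score distribution, so this part is assumption. Take independent prevalences of age ≥75 60%, hypertension 80%, diabetes 33%, heart failure 25% and stroke/TIA 12%.
- None of the four one-point items: 0.40 × 0.20 × 0.67 × 0.75 = 0.0402.
- Exactly one: 0.0603 (age) + 0.1608 (hypertension) + 0.0198 (diabetes) + 0.0134 (heart failure) = 0.2543.
- No stroke and at most one item: 0.88 × (0.0402 + 0.2543) = 0.259.
- Of this, at most 0.88 × 0.0402 = 0.035 is ineligible, depending on sex and vascular prevalence. The share among eligible patients is therefore between (0.259 − 0.035)/(1 − 0.035) = 23% and 26%, or about 25%.

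A sicker assumed mix gives about 12% and a healthier one about 40%.

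**The case against.** The strongest reply is that this is a slip in one row of a variable table, with no certain effect on any result. CHADS2 is only a possible predictor. The covariate list is open, and CHADS2 overlaps heavily with CHA2DS2-VASc and with its own components, which are listed separately. A patient who scores 0 or 1 has a known score, and the protocol does not say that the grouped form is the one to be modelled. The gap would also show at once in a descriptive table.

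Most of that stands, and it limits the consequence. It does not remove the error. The bands are the only form given for CHADS2, whereas Table 1 says explicitly that age is also kept as continuous. Nor is this a detail left to a statistical analysis plan: the protocol fixes specific categories, and they do not cover its own eligible population.

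A reader might go further and infer that the primary analysis will lose these patients, or that its estimate of how stroke risk relates to treatment is cut off at the low end. The protocol does not support that. Loss depends on banded CHADS2 being offered to the model. Unless patients are actually dropped, CHA2DS2-VASc serves the same purpose and covers every eligible patient. Nor are those without a band simply the lowest-risk patients: their CHA2DS2-VASc runs from 2 to 4, which reaches the middle band.

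**Conclusion.** The CHADS2 categories in Table 1 are wrong as written. They leave out scores 0 and 1, which eligible patients can have, in 19 of 127 eligible component profiles. That count rests only on the protocol's definitions and on the inferred point weights, which reproduce both stated maxima. It counts profiles, not patients.

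The share of patients affected cannot be derived from the protocol. The 12% to 40% range shows that the gap need not be trivial, but it rests wholly on assumed independent prevalences and should not be quoted as an estimate.

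The baseline categories fail to sum to the cohort if the bands are used for reporting. Dropping or misplacing patients in the primary model depends further on the banded form being a candidate there. Eligibility, the ever-treated and never-treated counts, the CHA2DS2-VASc and age subgroups, and the secondary outcome definitions are untouched. This should be fixed, but it does not by itself put the primary objective at risk.

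**What to change.** In Table 1, CHADS2 row, replace the groups with ones that cover 0 to 6. The minimum change is to add a 0-1 band. Groups of 0-1, 2-3 and 4-6 would hold 19, 60 and 48 of the 127 eligible profiles. Merging the two top bands is optional: a band holding only the score 6 is awkward but not an error. Keep 2-3, 4-5 and ≥6 for CHA2DS2-VASc only.

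The cost is one line in one table, with no new data and no extra analysis.

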#### Apixaban

NON-INTERVENTIONAL STUDY PROTOCOL

Variable a	Role	Operational definition		
Congestive heart failure	Baseline characteristic and potential predictor	A flag will be created for patients with claims for congestive heart failure during the baseline period.		
Diabetes	Baseline characteristic and potential predictor	A flag will be created for patients with claims for diabetes in the baseline period.		
Hypertension	Baseline characteristic and potential predictor	A flag will be created for patients with claims for hypertension in the baseline period.		
Chronic Obstructive Pulmonary Disease (COPD)	Baseline characteristic and potential confounder	A flag will be created for patients with COPD claims during the baseline		
Renal disease	Baseline characteristic and potential predictor	A flag will be created for patients with claims for renal disease in the baseline period.		
Myocardial infarction	Baseline characteristic and potential predictor	A flag will be created for patients with claims for myocardial infarction in the baseline period.		
Dyspepsia or stomach discomfort	Baseline characteristic and potential predictor	A flag will be created for patients with claims for dyspepsia or stomach discomfort in the baseline period.		
Peripheral arterial disease	Baseline characteristic and potential predictor	A flag will be created for patients with claims for peripheral arterial disease in the baseline period.		
Transient ischemic attack	Baseline characteristic and potential predictor	A flag will be created for patients with claims for transient ischemic attack in the baseline period.		
Coronary artery disease Baseline characteristic		A flag will be created for patients with claims for coronary artery disease in the baseline period.		

Do not distribute for purposes outside of specific activities related to development of FDAMAs114 compliant pieces. Content within this protocol is subject to change based on communication planning and input by external review committees.

#### Apixaban

NON-INTER	VENTIONAL	STUDY	PROTOCOL
HOI IN LICE		DIODI	ROTOCOL

Variable a Role		Operational definition		
	and potential predictor			
History of falls Baseline characteristic and potential predictor		A flag will be created for patients with claims for fall(s) in the baseline period.		
Baseline medication use	Baseline characteristic and potential predictor	Individual flags will be created for patients with prescription claims for angiotensin converting enzyme inhibitors, amiodarone, angiotensin receptor blockers, beta blockers, H2-receptor antagonists, proton pump inhibitors, anti-platelets, statins, nonsteroidal anti-inflammatory drugs (NSAIDs), inhibitors of warfarin, inducers of warfarin, dronedarone, digoxin, calcium channel blockers, renin angiotensin system antagonists, glucocorticoids, diuretics, metformin, sulfonylureas, thiazolidinedione, insulin, other diabetes drugs, antiulcer agents, and antidepressant.		
Index dose of NOAC Baseline characteristic		The index dose of the NOAC will be evaluated and categorized as standard (5mg apixaban, 150mg dabigatran, 60mg edoxaban, and 20mg rivaroxaban,) or low dose (2.5mg apixaban, 75mg dabigatran, 30mg edoxaban, and 10 or 15mg rivaroxaban,)		
Baseline all-cause health care Baseline costs characteristic		All-cause health care costs in the baseline period will be computed for inpatient, office, outpatient hospital, ER, pharmacy, DME, SNF, HHA, and hospice costs. Costs will be adjusted to 2016 US dollars using the medical care component of the CPI. Total medical and total health care costs will be calculated.		
Baseline all-cause health care utilization	Baseline characteristic	All-cause health care utilization in the baseline period will be computed for inpatient admissions, office visits, outpatient hospital visits, ER visits, pharmacy use, DME, SNF, HHA, and hospice use.		

a Unless specified, all primary and secondary diagnosis codes will be used.

Do not distribute for purposes outside of specific activities related to development of FDAMAs114 compliant pieces. Content within this protocol is subject to change based on communication planning and input by external review committees.

#### Apixaban

Table 2. Clinical and Treatment Pattern Outcome Variables					
Variable	Role	Operational Definition			
Stroke/SE	Outcome	Stroke/SE will be identified using hospital claims with a stroke/SE diagnosis code as the first listed ICD-9-CM or ICD-10-CM code. Stroke/SE will be classified into 3 categories: ischemic stroke, hemorrhage stroke, and SE. Time to stroke/SE will be defined as the number of days from index date to the occurrence of the first stroke/SE requiring hospitalization.			
Major bleeding	Outcome	Major bleeding will be identified using hospital claims with a bleeding diagnosis code as the first listed ICD-9-C or ICD-10-CM diagnosis or procedure code.  Time to major bleeding will be defined as the number of days from index date to the occurrence of the first major bleeding event requiring hospitalization. Major bleeding may be further stratified by gastrointestinal and intracranial hemorrhages and other major bleeding.			
Death	Outcome	Death information from the database will be used. Time to death will be defined as the number of days from index date to death.			
Discontinuation (Treated Patients)	Outcome	Treated patients will be considered to have discontinued if there was no additional refill for the index anticoagulant after 30 days of the previous prescription's run-out date.  The discontinuation date will be defined as the run-out date plus 30 days.			
Time to discontinuation (Treated Patients)	Outcome	Time to discontinuation will be defined as the number of days from the OAC prescription index date to the discontinuation date.			
Switch among anticoagulants (Treated Patients)	Outcome	A switch among anticoagulants will be defined as a prescription filled for non-index anticoagulants within 30 days before or after the run-out date.  Time to switch will be defined as the number of days from the OAC prescription index date to the first prescription date of the switch.			
Time-to-switch (Treated Patients)	Outcome	Time to switch will be defined as the number of days from the OAC prescription index date to the switch date.			

Table 2, Clinic	cal and Treatment Patt	ern Outcome Variables
	cal and frequencine i acc	

Do not distribute for purposes outside of specific activities related to development of FDAMAs114 compliant pieces. Content within this protocol is subject to change based on communication planning and input by external review committees.

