# 8.2. Setting

Ever treated with OAC and never treated with OAC patients will be selected from 01JAN2013-31DEC2016. To ensure access to the patients' complete medical history, they will be required to have continuous health plan enrollment for the 12 months before the first AF diagnosis date/index date (baseline period). Patient data will be assessed from index date until the earliest of death, health plan disenrollment, treatment switch (treated patients), discontinuation (treated patients), or 31DEC2016 (end of study).

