# 8.2.3. Cohorts

Patients eligible according to the above criteria will be assigned to the following cohorts:

Do not distribute for purposes outside of specific activities related to development of FDAMAs114 compliant pieces. Content within this protocol is subject to change based on communication planning and input by external review committees.

Apixaban NON-INTERVENTIONAL STUDY PROTOCOL

- 1) Ever-Treated Cohort: NVAF Patients had ≥1 pharmacy claim for apixaban, dabigatran, edoxaban, rivaroxaban, or warfarin from 01JAN2013-31DEC2016 on or after the first AF diagnosis
  - a. Apixaban cohort: Patients who initiated with apixaban on or after index date
  - b. Dabigatran cohort: Patients who initiated with dabigatran on or after index date
  - c. **Edoxaban cohort:** Patients who initiated with edoxaban on or after index date. Given the small sample size, edoxaban patients will not be included in the secondary clinical and healthcare utilization and costs analyses.
  - d. Rivaroxaban cohort: Patients who initiated with rivaroxaban on or after index date
  - e. Warfarin cohort: Patients who initiated with warfarin on or after index date
- 2) Never-Treated Cohort: NVAF patients with no pharmacy claim for an OAC from 01JAN2013-31DEC2016

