# 8.4. Data Sources

#### Medicare Inpatient Data

The inpatient claim file contains final action claims data submitted by inpatient hospital providers for facility cost reimbursement. Information therein includes ICD-9-CM diagnosis and ICD-9 procedure codes, ICD-10-CM diagnosis and ICD-10 procedure codes, Diagnosis Related Groups, dates of service, reimbursement amounts, hospital providers, and beneficiary demographic information. All file observations are at the claim level.

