# Medicare PDE Data

The Medicare PDE data contains prescription drug costs and payment data that enable CMS to make payments to the plans and otherwise administer Part D benefits. When a beneficiary fills a prescription under Medicare Part D, a prescription drug plan sponsor must submit a summary record to CMS. Unlike individual drug claim transactions, the PDE data are summary extracts using CMS-defined standard fields.

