# Skilled Nursing Facility

The SNF file contains final action FFS claims data submitted by SNF providers. This file includes ICD-9-CM and ICD-10-CM diagnosis and procedure codes, dates of service, reimbursement amount, SNF provider number, and beneficiary demographic information.

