# 8.8. Subgroup and Sensitivity Analysis

Additional subgroup and sensitivity analyses will be conducted, including:

- high-risk CHA2DS2-VASc score subgroups, specifically, 2-3, 4-5, and ≥6 (primary objective): assess whether the predictors of treatment would be impacted by baseline CHA2DS2-VASc score.
- high-risk age subgroups, specifically, 65-74, 75-79, and  $\geq$ 80 years (primary objective): assess whether the predictors of treatment would be impacted by age.
- censor patients at 6 months (secondary clinical objectives): assess whether the differential follow-up time in each cohort would affect the clinical outcomes.
- use a certain allowable gap for drug exposure, such as 14 days (secondary clinical objectives): assess whether the allowable gap in OAC days of supply for treated patients would have an impact on the clinical outcomes, since a shorter allowable gap will increase the likelihood of having the patients truly on treatment.
- multivariable Cox regression (secondary clinical objectives): assess whether statistical methods on the multivariable analysis would affect the clinical outcomes.
- adjusting for the competing risks of death (secondary clinical objectives): assess whether death is a competing risk in the clinical outcome analyses.

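### The refill-only discontinuation rule ignores inpatient and skilled nursing stays, can record a stop in a patient who missed no dose, and is checked only by an analysis that adds such false stops

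*Protocol*

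**What the plan says.** - **Rule and date.** Section 8.3, Table 2: a treated patient has "discontinued if there was no additional refill for the index anticoagulant after 30 days of the previous" prescription's run-out. "The discontinuation date will be defined as the run-out date plus 30 days".
- **Consequence.** Section 8.2 ends follow-up at the earliest of several events, including "treatment switch (treated patients), discontinuation (treated patients), or 31DEC2016 (end of study"). The Abstract (Population) and section 8.7 (time-varying Cox models) instead give the off-treatment time of ever-treated patients to the untreated side.
- **Source of exposure.** Section 8.2.3 defines OAC use by a "pharmacy claim for apixaban, dabigatran, edoxaban, rivaroxaban, or warfarin from 01JAN2013-31DEC2016 on or after the first AF diagnosis". Section 8.4 says how a drug record arises: "When a beneficiary fills a prescription under Medicare Part D, a prescription drug plan sponsor must submit a summary record to CMS".
- **Facility files.** Of the SNF file, section 8.4 says: "This file includes ICD-9-CM and ICD-10-CM diagnosis and procedure codes, dates of service, reimbursement amount". Of the inpatient file: "The inpatient claim file contains final action claims data submitted by inpatient hospital providers for facility cost reimbursement". Both list service dates. Neither description lists drugs given.
- **Planned check.** Section 8.8 would "use a certain allowable gap for drug exposure, such as 14 days". No longer gap is planned, and no analysis accounts for facility stays.
- **Limitations.** Section 8.10 mentions incomplete claims information in general terms and does not name facility stays.

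**The concern.** Days' supply is counted from the fill date as if the patient took the drug from that bottle every day. In a facility that supplies the drug, the home supply is not used and no new fill is needed. The calculated run-out passes, the 30-day allowance passes, and the rule records a stop. The gap then reflects where the drug came from, not whether the patient was taking it.

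Time to discontinuation, itself a listed outcome, becomes too short. Treated time and events after run-out plus 30 days either leave the analysis (section 8.2) or are credited to untreated time (Abstract, section 8.7). The same holds for inpatient and SNF costs in that period, which Table 3 includes in all-cause costs. Only treated patients can be misclassified in this way. The primary objective is not affected, because ever-treated status needs only one claim.

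**Working it through.** The protocol gives no figure to reproduce, so the check applies the Table 2 rule to possible stays.

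**Inputs from the protocol:** allowable gap G = 30 days (Table 2), or 14 days (section 8.8); stop dated at run-out + 30.

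**Assumptions:** a supply of S days is filled on day 0, with S = 30 or 90. Admission falls on day a = 0, …, S − 1 with equal weight. The stay lasts L days, the facility gives the OAC throughout, and no Part D fill occurs during the stay.

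**One patient.** S = 30, admission on day 20, discharge on day 70, so L = 50.
- Calculated run-out: day 30. Recorded stop: 30 + 30 = day 60.
- Home supply left at admission: 30 − 20 = 10 days. Refill due: 70 + 10 = day 80.
- Gap: 80 − 30 = 50 days, which exceeds 30 with no dose missed.
- With a refill on the day of discharge instead, the gap is 70 − 30 = 40 days, still over 30.
- Days 20 to 60 stay treated. The part of the stay cut off is 70 − 60 = 10 of 50 days.

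**General case.**
- Case A, leftover supply used first: the next fill is on day S + L, so the gap is L. A stop is recorded whenever L > G.
- Case B, refill on the day of discharge: the gap is a + L − S. A stop is recorded when a > S + G − L, so the share of admission days affected is (L − G − 1)/S, limited to the range 0 to 1.

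| G | S | L | Case A | Case B |
|---|---|---|---|---|
| 30 | 30 | 31 | stop | 0/30 = 0% |
| 30 | 30 | 45 | stop | 14/30 = 47% |
| 30 | 30 | 60 | stop | 29/30 = 97% |
| 30 | 30 | 75 | stop | 100% |
| 30 | 90 | 31 | stop | 0/90 = 0% |
| 30 | 90 | 45 | stop | 14/90 = 16% |
| 30 | 90 | 60 | stop | 29/90 = 32% |
| 30 | 90 | 90 | stop | 59/90 = 66% |
| 14 | 30 | 31 | stop | 16/30 = 53% |
| 14 | 90 | 31 | stop | 16/90 = 18% |

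With G = 30, no stay of 30 days or less gives a false stop in either case. With G = 14, case A begins at L = 15. In case B a 31-day stay goes from 0% to 53% (S = 30) or 18% (S = 90). Shortening the gap can only add false stops of this kind.

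**With run-out extended by the stay.** In the example, run-out becomes 30 + 50 = day 80. The gap is 0 in case A, and in case B the day-70 fill comes before run-out. No stop is recorded, and the same holds for any L.

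**The case against.** The strongest reply is that adjusting days' supply for facility stays is a programming detail that an analysis plan may settle. That would carry weight if the protocol had left the rule open. It states the rule, the stop date and the only sensitivity analysis of the gap, and these produce the error when applied as written.

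Other points stand and limit the concern:
- The protocol nowhere says that facility-supplied OAC is absent from the Part D data. This is inferred from the file descriptions, and it covers only the inpatient and SNF stays whose files are held.
- A reader might infer that any stay over 30 days is recorded as a stop. The trigger is the gap after run-out, not the length of stay. With a refill at discharge, a 31-day stay is never affected.
- A reader might also infer that the error must flatter OAC treatment, because sick patients' events leave treated time. The protocol does not support that. Time up to run-out + 30 stays treated. Censoring removes person-time as well as events. Stroke/SE and major bleeding count only as first-listed codes on hospital claims, so an event arising during a stay for another reason may not be captured in either group. Death is more exposed, but the protocol gives no rates.
- The censoring weights in section 8.7 may offset part of any informative censoring. They do not repair misclassified exposure.
- The 14-day gap is only an example, and its stated aim is to make it more likely that patients are truly on treatment. That is a fair aim, but it leaves false stops untested.

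**Conclusion.** The point holds in limited form. The rule can record a stop in an uninterrupted user, and the one planned gap analysis makes this more frequent. Given a long stay with facility-supplied drug, the error is certain from 31 days if leftover supply is used first. If the refill comes at discharge, it ranges from 0% at 31 days to 97% at 60 days for a 30-day supply, and from 0% to 32% for a 90-day supply. These shares rest on the inference about the Part D data and on the assumed supply lengths and uniform admission day.

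The number of patients affected and the net effect on any hazard ratio or cost comparison cannot be computed, because the protocol gives no distribution of stay lengths or days' supply. Whether the misclassified time is dropped or credited to untreated depends on which of section 8.2 and the Abstract with section 8.7 governs, a separate conflict that this rule does not cause. The secondary objectives on outcomes and costs and the treatment-pattern outcomes are affected; the predictors of treatment are not.

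**What to change.** In section 8.8, add an analysis that moves the run-out date later by the inpatient and SNF days falling within the supply period or the allowable gap, using the service dates already held, and then applies the 30-day (and 14-day) rule. Repeat the count until the date no longer moves. In the example, days 20 to 60 first add 40 days (run-out day 70), and days 60 to 70 then add 10 more (run-out day 80). Report time to discontinuation and the secondary comparisons with and without the extension, and name the limitation in section 8.10.

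The cost is programming on files the study already has. The drawback is that a patient whose OAC was truly stopped in the facility is carried as treated for those days. For that reason the extension is better as an added analysis than as the only rule: the two versions bracket the exposure assumption, with dosing continued throughout the stay in one and the stop recorded from refills alone in the other.
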